11.3 Clinical Laboratory Evaluation

Laboratory parameters (hematology, serum chemistry, and urinalysis) will be summarized using descriptive statistics at Baseline and at each post-baseline time point by treatment group.

Changes from Baseline will also be summarized. Refer to the list of laboratory tests to be performed in [Appendix 2](#).

In addition, shift tables will be provided to assess changes in laboratory values from Baseline to the most extreme post-baseline value using clinically notable reference ranges to derive if a laboratory measurement as low, normal, or high compared to the reference ranges.

Selected laboratory parameters (refer to [Appendix 3](#)) will be graded according to NCI CTCAE v5.0¹. The number and percentage of patients with CTCAE Grade ≥ 3 laboratory values will be summarized by treatment group.

The number and percentage of patients with clinically significant laboratory test findings will also be summarized by treatment group and visit. This will be done by laboratory category and laboratory parameter, as well as by overall.

Serology test and serum pregnancy test results at screening will be listed only.

11.4 Vital Signs

Vital sign data will be summarized by presenting summary statistics for observed and change from Baseline values, by visit and treatment group. Temperature will be collected in °C (Celsius) or °F (Fahrenheit) in eCRF, all values will be converted to °C for analysis.

The °F values will be converted using the formula given below.

$$^{\circ}\text{C} = (^{\circ}\text{F} - 32) * /9$$

Descriptive statistics for the following vital signs will be presented:

- Systolic blood pressure (mmHg)
- Diastolic blood pressure (mmHg)
- Heart rate (beats/min)
- Respiration rate (breaths/min)
- Body temperature (°C)

The incidence rates of vital sign abnormalities (refer to [Appendix 4: Criteria for Abnormal Values for Vital Signs](#)) will be summarized by treatment group. A second summary table will also be produced, summarizing the incidence rates of vital sign abnormalities by treatment group and visit.

The incidence rates of clinically significant vital signs will be summarized by treatment group, as well as by treatment group and visit.

A data listing of vital signs will also be created.

11.5 Physical Examination

A complete physical examination will include but not limited to the evaluation of the following organs or body systems: skin; head, eyes, ears, nose, and throat; thyroid, respiratory, cardiovascular, and central nervous systems, abdomen (liver and spleen), lymph nodes, and extremities.

Abnormal findings on physical examination prior to signing of informed consent will be included in medical history CRF whereas abnormal findings started after the signing of informed consent will be included in AE CRF.

Physical examination results will be included in data listings only.

11.6 12-Lead ECG

Values for the following 12-lead ECG parameters and change from Baseline values will be summarized through descriptive statistics by treatment group and visit.

- PR interval (sec)
- RR interval (msec)
- QRS interval (msec)
- QT interval (msec)
- Corrected QT interval (msec)

Three ECGs with 1-3 min interval will be performed before 1st dose on Day 1 only, and for data recorded on continuous scale, the means of the 3 ECGs will be used as Baselines and overall interpretation will be presented as the most severe (worst case) of the respective readings for Baseline. A single ECG will be performed for all other time points.

All ECGs must be evaluated by the Investigator and assessed as normal or abnormal, including the clinical significance (Yes/No) of abnormal values. The number and percentage of patients with clinically significant abnormal interpretation of ECGs will also be summarized by treatment group and visit.

The maximum increase in corrected QT interval from Baseline will be summarized through descriptive statistics by treatment group.

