**Secondary Outcome Measures:****Safety Endpoints:**

- Proportion (%) of patients with any AEs, SAEs and drug-related AEs during the study (Baseline to Day 14 and Day 28)
- Proportion (%) of patients with clinically significant abnormality in clinical laboratory tests and ECG during the study (Baseline to Day 14 and Day 28)
- Change in parameters for coagulopathy including [REDACTED] during the study (Baseline to Day 14 and Day 28)
- Change in parameters of cardiac function including [REDACTED] during the study period (Baseline to Day 14 and Day 28)

Changes in safety outcomes in patient populations with different Baseline levels of inflammatory biomarkers to assess the correlation of biomarker profile to safety outcomes.

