### ***12-Lead Electrocardiograms***

Values for 12-lead ECG parameters (RR, PR, QRS, QT, and corrected QT interval) and change from Baseline values will be summarized through descriptive statistics by treatment group and visit. The number and percentage of patients with clinically significant ECG findings will also be summarized by treatment group and visit. The maximum increase in corrected QT interval from Baseline will be summarized.

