4 OUTCOME MEASURES

Objectives	Outcome Measures
Primary	
Primary Objective: 
 • To assess the overall safety and tolerability of SIR1-365 in patients with severe COVID-19 	Primary Safety Measure: 
 • Proportion (%) of patients with any treatment-emergent adverse events (TEAEs) during the treatment period (Baseline to Day 14). Secondary Safety Measures: 
 • Proportion (%) of patients with any adverse events (AEs), serious adverse events (SAEs), and drug-related AEs during the study (Baseline to Day 14 and Day 28) • Proportion (%) of patients with clinically significant abnormality in clinical laboratory tests and electrocardiogram (ECG) during the study (Baseline to Day 14 and Day 28) • Change in parameters for coagulopathy including D-dimer, fibrinogen, coagulation tests, and platelet count during the study (Baseline to Day 14 and Day 28) • Change in parameters of cardiac function including NT-proBNP (or BNP) and high-sensitivity cardiac troponin during the study period (Baseline to Day 14 and Day 28) 
Changes in safety outcomes in patient populations with different Baseline levels of inflammatory biomarkers to assess the correlation of biomarker profile to safety outcomes.

Secondary	
Secondary Objectives: 
 1) To assess the clinical efficacy of SIR1-365 in patients with severe COVID-19 	Clinical Efficacy Endpoints: 
 • Change from Baseline to Day 7 and Day 14 in PaO₂/FiO₂ ratio

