14.3.7.4	Number and Percentage of Patients with Clinically Significant Vital Signs Parameters
14.3.7.5	Number and Percentage of Patients with Clinically Significant Vital Signs Parameters by Visit
14.3.8	12-Lead ECG Data
14.3.8.1	Summary of 12-Lead ECG Parameters by Visit
14.3.8.2	Number and Percentage of Patients with Clinically Significant Abnormal Values of ECG Interpretation by Visit
14.3.8.3	Maximum Increase in Corrected QT Interval from Baseline
14.3.9	Coagulopathy Data
14.3.9.1.1	Summary of Coagulopathy Results by Visit
14.3.9.1.2	Summary of Coagulopathy Results at Day 7, Day 14 and Day 28 (LOCF)
14.3.9.2.1	Coagulopathy Results, Normal Range Shift from Baseline
14.3.9.2.2	Coagulopathy Results, Normal Range Shift from Baseline to Last on Treatment Assessment
14.3.9.3	Summary of Coagulopathy Results, Time to First Time Back to Normal
14.3.10	Cardiac Function Damage Data
14.3.10.1.1	Summary of Cardiac Function Results by Visit
14.3.10.1.2	Summary of Cardiac Function Results at Day 7, Day 14 and Day 28 (LOCF)
14.3.10.2	Cardiac Function Results, Normal Range Shift from Baseline
14.3.11	Correlation of Baseline Inflammatory Biomarkers with Safety Endpoints
14.3.11.1	Association of Baseline Inflammatory Biomarkers with Treatment-Emergent Adverse Events
14.3.11.2	Association of Baseline Inflammatory Biomarkers with Serious Adverse Events

Figure Number	Figure Title
14.2.2.2	Kaplan Meier Curve of Time to Improvement of Oxygenation

14.2.4.4.1	Stacked Bar Chart for WHO Ordinal Scale Classification by Visit and Treatment
14.2.4.4.2	Stacked Bar Chart for WHO Ordinal Scale Classification by Visit and Treatment (LOCF)
14.2.9.1.7	Kaplan Meier Curve of Time to Reach 50% Reduction from Baseline in Plasma CRP Level
14.2.9.3.1	Boxplot for Inflammatory Biomarkers by Visit and Treatment
14.2.9.3.2	Boxplot for Inflammatory Biomarkers by Visit and Treatment (LOCF)
14.2.9.4.1	Mean (SD) Change in CRP from Baseline Over Time by Treatment
14.2.9.4.2	Mean (SD) Percentage Change in CRP from Baseline Over Time by Treatment
14.2.9.5.1	Mean (SD) Change in D-Dimer from Baseline Over Time by Treatment
14.2.9.5.2	Mean (SD) Percentage Change in D-Dimer from Baseline Over Time by Treatment
14.2.9.6.1	Mean (SD) Change in Ferritin and White Blood Cell Counts from Baseline Over Time by Treatment
14.2.9.6.2	Mean (SD) Percentage Change in Ferritin and White Blood Cell Counts from Baseline Over Time by Treatment

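### The secondary ECG safety endpoint is a per-patient proportion over the study to Day 14 and Day 28, but both analysis sections and the table list summarise it only by visit

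*SAP*

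**What the plan says.** **Endpoint.** The protocol synopsis lists among its secondary safety endpoints "Proportion (%) of patients with clinically significant abnormality in clinical laboratory tests and ECG during the study", with the windows Baseline to Day 14 and Day 28. Protocol section 4 repeats it. SAP section 4 carries it over: "patients with clinically significant abnormality in clinical laboratory tests and electrocardiogram (ECG) during the study (Baseline to Day 14 and Day 28".

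**Analysis.** Protocol 10.3.2, under 12-Lead Electrocardiograms, says: "The number and percentage of patients with clinically significant ECG findings will also be summarized by treatment group and visit". SAP 11.6 has the same plan: "The number and percentage of patients with clinically significant abnormal interpretation of ECGs will also be summarized by treatment group and visit". The only ECG summary there that pools over visits is continuous: "The maximum increase in corrected QT interval from Baseline will be summarized through descriptive statistics by treatment group".

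**Planned tables.** SAP Appendix 5 lists three ECG tables. Table 14.3.8.1 gives ECG parameters by visit, Table 14.3.8.2 is "Number and Percentage of Patients with Clinically Significant Abnormal Values of ECG Interpretation by Visit", and Table 14.3.8.3 gives the maximum QTc increase.

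**Neighbouring sections.** For vital signs, which this endpoint does not name, SAP 11.4 plans both forms: "The incidence rates of clinically significant vital signs will be summarized by treatment group, as well as by treatment group and visit". For laboratory findings, SAP 11.3 adds an overall summary to the by-visit one (Table 14.3.6.3.2).

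**The concern.** The endpoint has one proportion per arm for each window, with the patient as the unit. The planned analysis has one proportion per arm for each visit. A patient flagged on Days 7 and 10 appears in two columns, and two patients flagged once each produce the same two entries. The table cannot tell these cases apart.

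Safety is the primary objective of this study. If the plan is followed exactly, the report will hold no result for the ECG part of a declared secondary safety outcome. If someone derives the count after unblinding, SAP section 8 requires it to be labelled post hoc, which is an avoidable weakness for a safety outcome named in the protocol.

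**Working it through.** The documents give no rate, power or sample size for this endpoint, so there is no figure to reproduce. The check has three parts.

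**1. Does any planned output give the proportion?**

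| Output | Unit | Any-time count to Day 14 / Day 28? |
|---|---|---|
| Table 14.3.8.1 | ECG parameter values by visit | No |
| Table 14.3.8.2 | Patients flagged, by visit | No |
| Table 14.3.8.3 | Maximum QTc increase, continuous | No; not the binary endpoint |
| AE tables (SAP 11.2) | Patients by SOC and preferred term, onset windows of 14 and 28 days | No row isolates clinically significant ECGs |

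**2. Can it be recovered from Table 14.3.8.2?** The schedule has post-baseline ECGs on Days 7, 10, 14/EOT and 28. That is k = 3 visits for the first window and k = 4 for the second. Let a fraction p be flagged at every visit, with every patient having every ECG. The cumulative proportion then lies between

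- lower bound: p (the same patients each time), and
- upper bound: min(1, k × p) (different patients each time).

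Assumed per-visit rates, not from the documents:

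| p per visit | Through Day 14 (k = 3) | Through Day 28 (k = 4) |
|---|---|---|
| 5% | 5% to 3 × 5% = 15% | 5% to 4 × 5% = 20% |
| 8% | 8% to 3 × 8% = 24% | 8% to 4 × 8% = 32% |

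In counts, with the planned 30 patients per arm and 2 flagged at each visit (2/30 = 6.7%), the range is 2/30 to 6/30 (6.7% to 20.0%) through Day 14 and 2/30 to 8/30 (6.7% to 26.7%) through Day 28. One by-visit table fits every value in these ranges.

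Independence between visits is a case inside the range, not its upper end. At 5% it gives 1 − 0.95³ = 14.3% and 1 − 0.95⁴ = 18.5%.

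**3. Whom does each column describe?** Days 7 and 10 are in-hospital assessments, so those columns cover only patients not yet discharged. Early-discharge ECGs are tabulated with Day 14/EOT (SAP 8.4), so that column is broader. Day 28 may be a phone contact, which yields no ECG. By default, SAP section 8 leaves missing values out of percentages. The columns therefore have different denominators, and those for Days 7, 10 and 28 depend on discharge or return after randomisation. The Day 14/EOT and Day 28 columns also miss a finding seen only on Day 7 or Day 10.

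**The case against.** **The SAP follows the protocol.** This stands. Protocol 10.3.2 has the same by-visit plan. A reader might infer that the SAP departed from the protocol's analysis; it did not. The mismatch lies between the endpoint list and both analysis sections.

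**The endpoint could mean status at Day 14 and Day 28.** The laboratory/ECG item does not use the word any, as the AE item does. The coagulopathy and cardiac items use the same windows for changes that the SAP summarises by visit. On that reading two columns of Table 14.3.8.2 would suffice. The reading is possible but weaker: the item is a proportion of patients with an abnormality over the study from Baseline, and a point prevalence drops earlier findings.

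**AE tables capture these findings.** Partly. Under Protocol Appendix 4 a clinically significant ECG can be an AE, and AEs are tabulated with onset by 14 and 28 days. But such events are spread over preferred terms, and those judged to be expected disease progression are left out.

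**The count is recoverable.** This also stands. ECG data are listed by patient, and SAP Appendix 5 allows minor changes to the table index without an amendment. A reader might infer that the endpoint cannot be computed at all; the documents show only that no planned output computes it.

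**The problem is confined to ECG.** A reader might infer this from the laboratory overall table. SAP 11.3 does not support it: the wording may mean overall across parameters rather than across visits, and it names neither window.

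**By-visit percentages always understate the cumulative risk.** This is another tempting inference, and it holds only with stable denominators. If 2 of 10 patients still in hospital are flagged (20%) and no one else ever is, the cumulative figure among 30 treated patients is 2/30 = 6.7%.

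**Conclusion.** The point holds. The endpoint lists name a per-patient proportion with a clinically significant ECG abnormality through Day 14 and Day 28, and no planned table gives it. The textual part rests on reading the item as cumulative, which is the better reading though not the only one.

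The size is indeterminacy rather than a bias in a known direction. With 5% flagged at each visit, the plan's own table would fit anything from 5% to 15% by Day 14 and from 5% to 20% by Day 28; with 8%, anything from 8% to 24% and from 8% to 32%. These figures assume the rates and complete ECGs. Missed visits would change them and would make the table harder to interpret.

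The study is exploratory, with about 60 patients, and no primary analysis is affected. The change should still be made, because a declared secondary safety endpoint otherwise has no prespecified result.

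**What to change.** Add one table to SAP 11.6 and Appendix 5, by treatment group in the safety set: patients with at least one post-dose clinically significant abnormal ECG through Day 14 and through Day 28, as count and percentage. Specify:

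- the all-treated denominator and, beside it, the number with at least one post-baseline ECG in each window, so that patients never measured are not silently counted as event-free;
- a separate row for patients without such a finding at Baseline;
- that unscheduled and repeat ECGs count in this table, as a stated exception to SAP 8.5, which otherwise keeps them out of summaries.

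Keep Table 14.3.8.2 as supportive. In SAP 11.3, state that the laboratory overall table pools over visits in the same two windows. A between-group difference with 95% CI is optional, since the protocol plans only a descriptive ECG summary.

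The cost is one table from data already collected and a clarifying sentence in 11.3, both to be in place before unblinding.

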### 8.2.5. 12-Lead ECGs

TriPLICATE ECG tests with 1-3 min interval in between will be obtained on Day 1 before the 1st dose, and the mean of the 3 ECG tests will be used as the baseline. A single ECG is required before the 2nd dose on other days. All ECGs will be performed after the patient has been resting in a supine position for at least 5 minutes.

Outputs from the local ECG machine will be used in this study. All ECGs must be evaluated by the Investigator. Clinically significant abnormal ECGs may be repeated at the discretion of the Investigator.

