Informed consent	X									
Medical history	X									
Demographics	X									
Physical examinations	X ⁴								X	
Vital signs ⁵	X	X	X	X	X	X	X	X		X

12-lead ECG	X	X ⁶		X		X		X	X
Blood samples for routine lab tests including CRP and ferritin ⁷	X	X	X	X	X	X	X	X	X
Blood samples for coagulopathy and cardiac panels ⁸		X	X	X		X		X	X
Urine sample for urinalysis	X	X	X	X		X		X	X
Serum serology and pregnancy tests for screening	X								
Inclusion and exclusion	X								
Randomization		X							
Treatment		X	X	X	X	X	X	X	
Oxygen use and saturation (pulse oximetry)	X	X	X	X	X	X	X	X	X
PaO ₂ /FiO ₂ ratio	X	X		X				X	
WHO ordinal scale		X		X				X ¹³	X
Blood sample for cytokine/chemokine panels and CV biomarkers ⁹		X		X				X	
Blood sample for PK analysis and pRIP1/pMLKL assay ¹⁰		X		X				X	
Urine sample for NGAL and KM-1 assay ¹¹		X		X				X	
AE and ConMed	X	X	X	X	X	X	X	X	X

1. Enrollment and Baseline. Screening and Baseline visits can be combined. ECG, laboratory test and other test results taken within 24 hours prior to consent will be used as Baselines.
2. End of Treatment (EOT) or early discharge.
3. End of the study (EOS) or early discontinuation.
4. For enrolled patients, physical examination obtained at screening will be the Baseline. Weight and height will be measured at screening.
5. Vital signs will be taken before the 1st dose on Day 1 as Baseline, and within 3 hours before the 2nd dose on other days.
6. Three ECGs with 1-3 min interval before the 1st dose on Day 1 only, and the means of the 3 ECGs will be used as Baselines. ECGs will be done within 3 hours before the 2nd dose on other days. Local ECG machine will be used in this study.
7. Routine laboratory tests before the 2nd dose will be done daily at local labs. CRP and ferritin tests will be done on Days 1, 3, 7, 10 and 14.
8. Coagulopathy panel including D-dimer, fibrinogen, PT, PTT and INR, and cardiac function panel including NT-proBNP (or BNP) and high-sensitivity cardiac troponin will be done on Days 1, 3, 7, 10 and 14 at local labs with samples collected before the 2nd dose.
9. One blood sample collected before the 1st dose on Day 1 and before the 2nd dose on Days 7 and 14 for cytokine/chemokine panels and CV biomarker assays to be conducted at a central lab

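### No QTc correction formula is named and local ECG machine output is used, so the correction is uncontrolled; SAP 11.6 should derive one QTcF from the recorded QT and RR

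*SAP*

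**What the plan says.** Protocol 8.2.5 states: "Outputs from the local ECG machine will be used in this study". Footnote 6 to the SAP schedule (Table 5.2) repeats it: "Local ECG machine will be used in this study".

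The protocol's safety analysis (10.3.2, 12-Lead Electrocardiograms) has "Values for 12-lead ECG parameters (RR, PR, QRS, QT, and corrected QT interval) and change from Baseline values will be summarized". SAP 11.6 lists the same five parameters, with RR, QT and corrected QT in milliseconds. For the three pre-dose tracings on Day 1, SAP 11.6 specifies that "the means of the 3 ECGs will be used as Baselines". Later time points have one ECG each. Both documents then summarise the largest rise in corrected QT; the SAP wording is "The maximum increase in corrected QT interval from Baseline will be summarized through descriptive statistics by treatment group".

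Neither document names a correction formula, asks for QTc to be calculated from QT and RR, describes a central read, or requires sites to use the same formula. SAP 12.3 shows that sites are in the USA, Mexico and Pakistan.

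**The concern.** QTc is a calculated quantity, and different formulas give different values for the same tracing. When the formula is whatever the local machine uses, the analysis variable is not defined. A reader of the ECG tables could not say what a given QTc change means.

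The choice matters most when heart rate changes between baseline and follow-up. Bazett's formula over-corrects at high rates if QT follows a cube-root relation to RR. A patient who is fast at baseline and slows with recovery would then show a falling QTc with no drug effect, and a real prolongation of similar size could be cancelled in that patient's change from baseline. A patient who deteriorates and speeds up would show the reverse. High baseline rates are possible here, since a heart rate of 125 or more is one of the signs that can satisfy inclusion criterion 3.

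The primary objective is safety, and QT and RR are already among the analysed parameters, so leaving the formula open is an avoidable weakness.

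**Working it through.** The documents give no QTc figure, threshold or expected heart rate, so there is no figure of the plan's own to reproduce. The check asks how far printed QTc moves when only heart rate changes.

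**Inputs**
- From the documents: local machine output, no formula named, QT and RR both summarised (protocol 8.2.5 and 10.3.2; SAP Table 5.2 and 11.6).
- Assumed: no drug effect; QT follows the cube-root relation, so QTcF is constant at 400 ms (range 380 to 440 ms); illustrative heart rates.

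**Formulas** (RR = 60/HR, in seconds)
- True QT = QTcF × RR^(1/3)
- Bazett: QT/RR^(1/2) = QTcF × RR^(-1/6)
- Hodges: QT + 1.75 × (HR - 60)
- Framingham: QT + 154 × (1 - RR)

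**Worked case, 110 to 80 bpm, Bazett**
- At 110: RR = 0.5455; 400 × 0.5455^(-1/6) = 442.5 ms
- At 80: RR = 0.75; 400 × 0.75^(-1/6) = 419.6 ms
- Change: 419.6 - 442.5 = -22.9 ms

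**Change in printed QTc (ms) from heart rate alone**

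| Heart rate (bpm) | Bazett at 400 | Bazett, 380 to 440 | Hodges at 400 | Framingham at 400 | Fridericia |
|---|---|---|---|---|---|
| 90 to 75 | -12.8 | -12.2 to -14.1 | -4.4 | +1.4 | 0 |
| 100 to 80 | -15.9 | -15.1 to -17.5 | -8.9 | +3.0 | 0 |
| 110 to 80 | -22.9 | -21.7 to -25.2 | -15.9 | +5.1 | 0 |
| 120 to 80 | -29.3 | -27.9 to -32.3 | -24.1 | +7.4 | 0 |

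The zero for Fridericia follows from the assumed cube-root relation. A rise from 80 to 110 bpm reverses the sign: +22.9 ms with Bazett.

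**When the shift passes 20 ms (Bazett, 400 ms).** The rate must fall from 90 to about 67.5, from 100 to about 75.4, from 110 to about 83.3, or from 125 to about 95.3 bpm. These are falls of roughly 22 to 30 bpm.

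**Difference between formulas on one tracing.** At 110 bpm and QTcF 400 ms, Bazett reads 442.5 - 400 = 42.5 ms higher than Fridericia.

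**A true +20 ms effect, 110 to 80 bpm, Bazett**
- Treated patient: 420 × 0.75^(-1/6) = 440.6; change 440.6 - 442.5 = -1.9 ms
- Placebo patient with the same heart rates: -22.9 ms
- Difference between arms: -1.9 - (-22.9) = +21.0 ms

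The within-patient change loses the effect; the contrast between arms keeps it.

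**If heart-rate change differs by arm.** Suppose both arms start at the same rate, with no drug effect, and end at 75 and 85 bpm. Bazett gives 415.2 and 423.9 ms, an artificial difference of 8.8 ms before rounding, in favour of the arm that slows more.

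**Limit of the remedy.** If QT actually follows the square-root relation with QTcB constant at 400 ms, then QTcF = 400 × RR^(1/6) and itself moves with rate: +13.9 ms for 100 to 80 bpm and +23.8 ms for 110 to 75.

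**The case against.** The strongest reply is that the plan leaves a formula unstated and nothing worse is shown. Its parts are as follows.

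- **Mixed formulas.** A reader might infer that sites use different corrections. The documents do not say which formula any machine prints. The annotated eCRF, which might define the field, is not among them. SAP Section 8 mentions ECG data as an example of external-vendor data, although no vendor or central read is described. Only an uncontrolled formula is supported. Even if sites do differ, a within-patient change is distorted by the mixture only if the machine or formula changes between visits; otherwise the mixture adds noise between sites.
- **A tachycardic population.** A reader might infer that patients enter with fast hearts. The heart-rate sign is one of several alternatives, and a patient can qualify on oxygenation, respiratory rate or imaging alone. No baseline heart rate is given.
- **Shifts above 20 ms as the rule.** This needs a Bazett machine (or, at 400 ms, Hodges from about 120 bpm) and a large fall in rate. The milder cases in the table stay below 20 ms.
- **A hidden drug effect.** Heart rate recovers in both arms, the trial is randomised and blinded, and ECG results are shown by arm, so the contrast largely survives, as the +21.0 ms example shows. Bias needs a different heart-rate change by arm. That is conceivable if the drug speeds recovery, but nothing in the documents establishes it.
- **Importance.** The listed ECG outcome measure is the proportion of patients with a clinically significant abnormality, as judged by the investigator. QTc change is a descriptive summary in an exploratory trial of about 30 patients per arm. Heart rate, RR and uncorrected QT are also summarised, so a rate imbalance would be visible.

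All of this limits the size and certainty of the point. It does not supply a definition of QTc, and the within-arm changes and maximum increases still rest on whatever correction the local machines apply.

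**Conclusion.** The point holds in a limited form. The QTc analysed in SAP 11.6 has no stated correction, comes from local machines, and may therefore follow different formulas at different sites. If Bazett is printed, a fall in heart rate alone moves it by about -13 to -23 ms over the falls from 90 to 75 and 110 to 80 bpm, and by more for larger falls. With Fridericia the shift is about 0. These figures assume a cube-root QT relation, a constant QTcF of 400 ms and illustrative heart rates; none of these comes from the documents.

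The consequence is that within-arm QTc changes and maximum increases can be understated in recovering patients and overstated in those whose heart rate rises. The documents do not support the stronger conclusions that formulas are in fact mixed, that shifts above 20 ms are typical, or that the randomised comparison would miss a real prolongation. This is a worthwhile correction to a secondary safety summary, not a threat to the primary outcome.

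**What to change.** In SAP 11.6, define QTcF = QT/RR^(1/3) with RR in seconds. The SAP lists RR in milliseconds, so divide by 1000 first. Calculate it for every ECG. At baseline, calculate it for each of the three tracings and then average. Use QTcF for all QTc summaries by visit, changes from baseline and maximum increases, and keep the machine-printed QTc in the listings. SAP 8.6 already standardises laboratory units because several laboratories are used; this is the same kind of step for ECGs.

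The cost is one derived variable and no new data, provided the eCRF holds QT and RR for each tracing, as their place among the summarised parameters implies. Make the change before unblinding, because SAP Section 8 labels analyses specified later as post hoc.

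The remaining drawback is that QTcF is not perfectly independent of heart rate. It gives one stated definition at every site and removes formula differences between machines, but it does not guarantee a zero rate effect. Counts of patients by QTcF category are an optional addition; this defect does not require them.
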